### **13.3 Description of analysis sets**

All Enrolled set will consist of all the subjects who signed informed consent to enter the study. Patient disposition and baseline characteristics and demography as well as analysis of the primary and secondary objectives will be based on the set.

All patients will be enrolled in 2 groups 1:1. The analyses of primary objective will be conducted based on the results in these groups:

- The investigated group will be consists of patients with clinical features of hereditary BC (according to NCCN breast and/or ovarian cancer genetic assessment guidelines V1.2017) and revealed clinically significant (pathogenic) germline mutations in DNA-repair genes (TP53 MLH1 MSH2 MSH6 PMS2 EPCAM APC MUTYH CDKN2A CDK4 ATM KIT PDGFRA CDH1 CTNNA1 PRSS1 SPINK1 BRCA1 BRCA2 FANCI FANCL PALB2 RAD51B RAD51C RAD54L RAD51D CHEK1 CHEK2 CDK12 BRIP1 PPP2R2A BARD1 PARP1 STK11 XRCC3) regardless morphological type, grade, receptor status and extent of the disease.

- The control group will be consisting of patients with sporadic BC without germline mutations in DNA-repair genes (TP53 MLH1 MSH2 MSH6 PMS2 EPCAM APC MUTYH CDKN2A CDK4 ATM KIT PDGFRA CDH1 CTNNA1 PRSS1 SPINK1 BRCA1 BRCA2 FANCI FANCL PALB2 RAD51B RAD51C RAD54L RAD51D CHEK1 CHEK2 CDK12 BRIP1 PPP2R2A BARD1 PARP1 STK11 XRCC3) regardless morphological type, grade, receptor status and extent of the disease.

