## **3. STUDY PLAN AND PROCEDURES**

### **3.1 Overall study design and flow chart**

This is a multicentre, non-interventional, prospective study to be carried out in representative oncology departments / institutions in order to determine the interrelation between the presence of germline DNA-repair genes mutations and PD-L1 expression level in tumour and immune cells in breast cancer. No additional procedures besides those already used in the routine clinical practice will be applied to the patients. Treatment assignment will be done according to the current practice.

It is planned to enroll approximately 240 subjects in 2 centers (Tatarstan Cancer Centre and Republican Clinical Oncological Dispensary Ufa).

PD-L1 expression in tumor and immune cells in FFPE tumor tissue samples estimated by IHC is the primary variable in this study. The primary variable value will be represented as “PD-L1 high” and “PD-L1 low”.

Genetic testing of germline mutations in DNA-repair system genes (NGS) in blood samples receiving on Screening/ Baseline Visit and PD-L1 expression testing (IHC) in FFPE tumor tissue samples will be carried out in Tatarstan Cancer Centre, Kazan.

The PD-L1 expression level in tumor and immune cells and number of TILs in FFPE tissue samples received prior to start of any antitumor treatment will be estimated in both groups.

The only one visit is planned for all patients in this study.

Information regarding patient demographics, the disease characteristics, and diagnostic tests results will be taken from the medical records.

Information about familial and individual oncological history will be received on the visit.

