### **13.4 Method of statistical analysis**

Considering the study objectives, the analysis strategy will be as follows:

A descriptive analysis approach will be used to analyse the study population, baseline data and clinical outcomes.

Descriptive statistics will include n, mean, median, standard deviation, minimum and maximum for continuous variables and n, frequency and percentage for categorical values. Proportion will be assessed together with 95% confidence interval, if applicable.

The assess of differences in pd-l1 high cases frequency between two groups and association of germline ddr-gene mutations and pd-l1 expression level will be performed by logistic regression with odds ratio calculation with 95% confidence interval

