## **14. DETERMINATION OF SAMPLE SIZE**

Today the data of PD-L1 expression level in breast cancer are limited. There are a few number of studies, which evaluated the frequency of PD-L1 expression in different breast cancer variants and the data of PD-L1 expression level in these studies are very differentiated depends on diagnostic approach, clone of antibodies and cut-off. We have calculated 2 variants of sample size based on minimal and maximal literature quantity data, using the Chi-squared statistic (or z test). Due to the absence of exact data about PD-L1 expression in hereditary and sporadic breast cancer we calculated the sample size based on data from general BC population (mainly is represented by sporadic BC) and TNBC (significant part of which is represented by hereditary BC). In the articles used as basis for calculation the authors assessed PD-L1 expression in tumor cells and the cut-off for PD-L1 positivity was 5%. In 2 studies estimated PD-L1 expression in total BC population as 4% and in TNBC as 11% the SP142 clone was used for IHC. We have found the only one study assessing concordance between SP142 and SP263 antibodies clones for IHC (on a subset of cases including BC) and the concordance was 95%. We are planning to assess the PD-L1 expression in both tumor and immune cells and use the 25% of PD-L1 positive cells as cut-off.

Considering the listed above we assume that the sample size will be near to a mean value between these two calculations.

Near 120 patients with breast cancer who have mutations in DNA-repair system genes and near 120 patients with breast cancer without mutations will be enrolled to the study in 2 centers:

Tatarstan Cancer Center, Kazan and Bashkortostan Clinical Oncology Center, Ufa. We will need to test near 390 patients for enrolling 240 patients (expected screen failure rate 35-40%). This data are based on the results of own pivotal study which has shown the frequency of clinically significant mutations in genes of DNA-repair system in familial BC 65%.

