#### Sample size (without continuity correction)

	N	Outcome+	Outcome-
Group 1:	221	24	197
Group 0:	221	9	212
Total:	442	33	409

3. Our assumption. If  $\alpha$  (two-tailed) =0,05,  $\beta$  =0,2, subject ratio in groups ( $q_1$  and  $q_2$ )=0,5/0,5, frequency of BC cases with high PD-L1 expression in sporadic BC group  $P_0=0,14$ , frequency of BC cases with high PD-L1 expression in hereditary BC group  $P_1=0,30$ , that OR 2,633, RR=2,114

The standard normal deviate for  $\alpha = Z_\alpha = 1.960$

The standard normal deviate for  $\beta = Z_\beta = 0.842$

Pooled proportion =  $P = (q_1 * P_1) + (q_0 * P_0) = 0,220$

$A = Z_\alpha \sqrt{P(1-P)(1/q_1 + 1/q_0)} = 1.624$

$B = Z_\beta \sqrt{P_1(1-P_1)(1/q_1) + P_0(1-P_0)(1/q_0)} = 0.684$

$C = (P_1 - P_0)^2 = 0.026$

Total group size =  $N = (A+B)^2/C = 208$

Continuity correction (added to N for Group 0) =  $CC = 1/(q_1 * |P_1 - P_0|) = 13$

That sample size can be calculated as:

Sample size (with continuity correction)			
	N	Outcome+	Outcome-
Group 1:	117	35	82
Group 0:	117	16	101
Total:	234	51	183

Sample size (without continuity correction)			
	N	Outcome+	Outcome-
Group 1:	104	31	73
Group 0:	104	15	89
Total:	208	46	162

References:

1. Злокачественные заболевания в России в 2015 г. (заболеваемость и смертность) / Под ред. А.Д. Каприна, В.В. Старинского, Г.В. Петровой. — М., 2015.
2. Kyle C. et al Association and prognostic significance of BRCA1/2-mutation status with neoantigen load, number of tumor-infiltrating lymphocytes and expression of PD-1/PD-L1 in high grade serous ovarian cancer

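### The 1:1 ratio is set only across both centres together and no centre term is named in the primary model, so the odds ratio is open to confounding by centre

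*Combined protocol and SAP*

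**What the plan says.** Section 13.3 gives one allocation statement for the whole study: "All patients will be enrolled in 2 groups 1:1. The analyses of primary objective will be conducted based on the results in these groups". Section 14 repeats it as a target for the two centres together: "Near 120 patients with breast cancer who have mutations in DNA-repair system genes and near 120 patients with breast cancer without mutations will be enrolled". No section sets a ratio, quota or matching rule within Kazan or within Ufa.

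Section 13.4 says that the comparison of PD-L1-high frequency "will be performed by logistic regression with odds ratio calculation with 95% confidence interval". It lists no covariates, strata or centre term. Section 13.1 promises a fuller analysis plan before database lock but does not say what it will contain.

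Two provisions bear on tissue handling. Section 3.1 centralises the assay: "PD-L1 expression testing (IHC) in FFPE tumor tissue samples will be carried out in Tatarstan Cancer Centre, Kazan". Inclusion criterion 4 (section 4.2) requires pre-treatment blocks that are suitable for PD-L1 immunohistochemistry. Section 13.3 accepts any histology, grade, receptor status and extent of disease in both groups.

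**The concern.** Carriers and controls are found, not allocated, so nothing in the design makes the centre mix the same in the two groups. One centre could supply most carriers and the other most controls while the overall 120/120 target is still met exactly.

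That matters only if PD-L1-high rates also differ by centre. There are two routes by which they could. One is case mix: section 2.2 itself asks whether PD-L1 varies with stage, receptor status, histology and grade, and none of these is balanced by design. The other is the handling of blocks at the source hospital before they reach the Kazan laboratory. If both conditions hold, part of a centre difference would be read as an effect of germline mutation, which is the study's primary question.

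**Working it through.** **1. The plan's own figure.** Section 14, third scenario: P0 = 0.14, P1 = 0.30, two-sided alpha 0.05, beta 0.20, equal groups, pooled P = 0.22.

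- A = 1.960 × √(0.22 × 0.78 × 4) = 1.624
- B = 0.842 × √(2 × 0.30 × 0.70 + 2 × 0.14 × 0.86) = 0.684
- C = 0.16² = 0.0256
- N = (1.624 + 0.684)² / 0.0256 ≈ 208, or 104 per group. The continuity correction adds 1/(0.5 × 0.16) = 12.5, giving about 117 per group.

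The stated figures reproduce. At 120 per group the power for 30% vs 14% is 85.4% (uncorrected two-sided z test). The calculation has no allowance for centre.

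**2. Bias with no centre term and no true association.** Let *hi* and *lo* be the PD-L1-high rates at the two centres and *k* the share of carriers from the higher-rate centre, with the mirror image for controls:

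- carriers: p1 = k·hi + (1 − k)·lo
- controls: p0 = (1 − k)·hi + k·lo
- spurious OR = [p1/(1 − p1)] / [p0/(1 − p0)]

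The centre rates and splits are assumptions. The pair 18%/10% averages 14%, the plan's control rate. The pair 28%/14% averages 21%, close to its pooled 22%.

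| Centre rates | k | p1 | p0 | Spurious OR | Rejection at nominal 5%, 120 per group |
|---|---|---|---|---|---|
| 18% / 10% | 0.50 | 0.140 | 0.140 | 1.00 | 5% |
| 18% / 10% | 2/3 | 0.153 | 0.127 | 1.25 | 9% |
| 18% / 10% | 0.75 | 0.160 | 0.120 | 1.40 | 14% |
| 28% / 14% | 0.50 | 0.210 | 0.210 | 1.00 | 5% |
| 28% / 14% | 2/3 | 0.233 | 0.187 | 1.33 | 14% |
| 28% / 14% | 0.75 | 0.245 | 0.175 | 1.53 | 26% |

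Example, last row: (0.245/0.755) / (0.175/0.825) = 0.3245/0.2121 = 1.53. Rejection is the probability that a two-sided pooled z test is significant when mutation has no effect.

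If *hi* = *lo*, then p1 = p0 for any k. If both groups share the same split, even 70/30 in each, then again p1 = p0. Bias needs both conditions together.

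**3. What a centre term costs in power.** Approximate effective size per group = 2 × Σ over centres of n1·n0/(n1 + n0), with 120 per group, then power for 30% vs 14%:

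| Carriers / controls, Kazan:Ufa | Effective n per group | Power |
|---|---|---|
| Same split in both groups | 120 | 85.4% |
| 60:40 / 40:60 | 115 | 83.9% |
| 70:30 / 30:70 | 101 | 78.7% |
| 80:20 / 20:80 | 77 | 67.1% |

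Example, 70:30 / 30:70: each centre contributes 84 × 36/120 = 25.2, so the effective size is 2 × 50.4 = 100.8.

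The centre term deals with the bias. Balance within centre protects the power.

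**The case against.** Section 13.4 is silent on covariates. It does not say that the model contains group alone, and an analysis plan is promised before lock. Centre is known for every patient, so a term could still be added. That stands as far as it goes: the accurate statement is that no centre term is named, not that the sponsor has ruled one out. But nothing commits the later plan to include one, and it cannot change the centre mix already enrolled.

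Some stronger readings are tempting, and the documents do not support them.

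- *Carrier yield differs between the centres.* Section 1.2 gives a Bashkortostan figure below 4%, but it is the frequency of one BRCA1 founder variant. There is no Tatarstan counterpart, and the study sequences a 35-gene panel. A different mutation spectrum does not imply a different total yield. The only yield figure, 65% in familial disease (section 14), is not split by centre.
- *Ufa blocks are handled differently.* Nothing says so. Staining in one laboratory with one antibody removes differences between staining laboratories, and inclusion criterion 4 screens out unsuitable blocks. These narrow the tissue route. They do not standardise fixation, processing or block age, and they do not touch case mix.
- *Centre could account for the whole effect the study is looking for.* The illustrated odds ratios stop at 1.53, well below the design value of 2.633. The 28% vs 14% pair is already nearly as wide as the plan's hypothesised mutation effect of 30% vs 14%, and mirror-image splits are an unfavourable choice.

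It is also fair to say that a two-level centre term is a weak stand-in for receptor status, grade, stage or age, all of which are recorded. Centre is one item in a general absence of named covariates. That is no reason to omit it.

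**Conclusion.** The point holds as a design weakness, not as a demonstrated bias. The ratio is fixed only over the two centres pooled, the primary model names no centre term, and the groups are not randomised. The planned odds ratio is therefore unprotected if carrier-to-control ratios and PD-L1-high rates both differ between Kazan and Ufa.

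Under the assumed centre rates and splits the spurious odds ratio is 1.25 to 1.53, and the nominal 5% test rejects in about 9% to 26% of studies. Both ranges rest wholly on those assumptions, because the documents give no centre-specific rate or split. With equal splits or equal rates there is no bias. The change should be made because the remedy is cheap and the enrolment part cannot be supplied after recruitment.

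**What to change.** **Section 13.4:** include centre (Kazan/Ufa) as a fixed term in the primary logistic regression, and tabulate PD-L1-high counts and rates by group within each centre.

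**Sections 13.3 and 14:** state an approximate 1:1 target within each centre, followed as a running count during recruitment. Patient-by-patient pairing is not advised. Carrier and control status both depend on sequencing results that arrive 1 to 3 months after day 0 (Table 1), so pairing would add delay to a one-year accrual, and validity does not require it once centre is in the model.

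**Cost:** one degree of freedom, and control recruitment at each centre paced to some extent by its carriers. With splits kept similar, power stays near 85% at the planned 240.

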### **13.4 Method of statistical analysis**

Considering the study objectives, the analysis strategy will be as follows:

A descriptive analysis approach will be used to analyse the study population, baseline data and clinical outcomes.

Descriptive statistics will include n, mean, median, standard deviation, minimum and maximum for continuous variables and n, frequency and percentage for categorical values. Proportion will be assessed together with 95% confidence interval, if applicable.

The assess of differences in pd-l1 high cases frequency between two groups and association of germline ddr-gene mutations and pd-l1 expression level will be performed by logistic regression with odds ratio calculation with 95% confidence interval

## **14. DETERMINATION OF SAMPLE SIZE**

Today the data of PD-L1 expression level in breast cancer are limited. There are a few number of studies, which evaluated the frequency of PD-L1 expression in different breast cancer variants and the data of PD-L1 expression level in these studies are very differentiated depends on diagnostic approach, clone of antibodies and cut-off. We have calculated 2 variants of sample size based on minimal and maximal literature quantity data, using the Chi-squared statistic (or z test). Due to the absence of exact data about PD-L1 expression in hereditary and sporadic breast cancer we calculated the sample size based on data from general BC population (mainly is represented by sporadic BC) and TNBC (significant part of which is represented by hereditary BC). In the articles used as basis for calculation the authors assessed PD-L1 expression in tumor cells and the cut-off for PD-L1 positivity was 5%. In 2 studies estimated PD-L1 expression in total BC population as 4% and in TNBC as 11% the SP142 clone was used for IHC. We have found the only one study assessing concordance between SP142 and SP263 antibodies clones for IHC (on a subset of cases including BC) and the concordance was 95%. We are planning to assess the PD-L1 expression in both tumor and immune cells and use the 25% of PD-L1 positive cells as cut-off.

Considering the listed above we assume that the sample size will be near to a mean value between these two calculations.

Near 120 patients with breast cancer who have mutations in DNA-repair system genes and near 120 patients with breast cancer without mutations will be enrolled to the study in 2 centers:

Tatarstan Cancer Center, Kazan and Bashkortostan Clinical Oncology Center, Ufa. We will need to test near 390 patients for enrolling 240 patients (expected screen failure rate 35-40%). This data are based on the results of own pivotal study which has shown the frequency of clinically significant mutations in genes of DNA-repair system in familial BC 65%.

1. If  $\alpha$  (two-tailed) =0,05,  $\beta$  =0,2, subject ratio in groups ( $q_1$  and  $q_2$ )=0,5/0,5, frequency of BC cases with high PD-L1 expression in sporadic BC group (based on the data in general population of BC)  $P_0=0,217$ , frequency of BC cases with high PD-L1 expression in hereditary BC group (based on the data in TNBC population, significant part of the letter is represented by HBC)  $P_1=0,559$ , that OR 4.574, RR= 2.576

The standard normal deviate for  $\alpha = Z_\alpha = 1.960$

The standard normal deviate for  $\beta = Z_\beta = 0.842$

Pooled proportion =  $P = (q_1 * P_1) + (q_0 * P_0) = 0.388$

$A = Z_\alpha \sqrt{P(1-P)(1/q_1 + 1/q_0)} = 1.911$

$B = Z_\beta \sqrt{P_1(1-P_1)(1/q_1) + P_0(1-P_0)(1/q_0)} = 0.768$

$C = (P_1 - P_0)^2 = 0.117$

Total group size =  $N = (A+B)^2/C = 61$

Continuity correction (added to N for Group 0) =  $CC = 1/(q_1 * |P_1 - P_0|) = 6$

That sample size can be calculated as:

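### Is the 80% power unsupported because 240 is not the mean of the two literature sample sizes and the hereditary rate was borrowed from TNBC?

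*Combined protocol and SAP*

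**What the plan says.** Section 14 states that exact PD-L1 data for hereditary and sporadic breast cancer do not exist. The control rate P0 is therefore taken from the general breast cancer population and the hereditary rate P1 from "TNBC (significant part of which is represented by hereditary BC"). The section adds that the source studies scored tumour cells and that "the cut-off for PD-L1 positivity was 5" per cent, whereas this study will count tumour and immune cells and "use the 25% of PD-L1 positive cells as cut-off". Section 13.3 enrols both groups "regardless morphological type, grade, receptor status and extent of the disease".

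Three calculations follow, all with two-sided alpha 0.05, 80% power and equal groups:

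| Calculation | P0 | P1 | Total N, uncorrected | Total N, continuity-corrected |
|---|---|---|---|---|
| 1 (literature, TNBC for P1) | 0.217 | 0.559 | 62 | 74 |
| 2 (literature, TNBC for P1) | 0.04 | 0.11 | 442 | 500 |
| 3 (labelled as the authors' own assumption) | 0.14 | 0.30 | 208 | 234 |

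The text preceding the calculations explains the choice of size by saying "we assume that the sample size will be near to a mean value between these two calculations". The third calculation prints its effect measures as "that OR 2,633, RR=2,114".

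**The concern.** Five things look wrong when the section is read closely.

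- That much of TNBC is hereditary does not make hereditary breast cancer mostly TNBC. The PD-L1 rate in carriers depends on the second proportion, and section 13.3 admits every receptor subtype.
- The planned 240 is not the average of the two literature totals.
- The pair 0.14 and 0.30 has no reference and is not the average of the source rates.
- The source rates use a 5% tumour-cell cut-off, while the endpoint uses 25% of tumour or immune cells.
- The printed relative risk does not match its own rates.

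If the true hereditary rate were nearer the control rate than planned, power would be below 80%, and a null result might be misread as evidence of no association.

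**Working it through.** **1. Reproduce the plan.** The section's formula is N = (A + B)²/C, with A = 1.960·√[P(1−P)·4], B = 0.842·√[2P1(1−P1) + 2P0(1−P0)], C = (P1−P0)², and P the mean of the two rates. The continuity correction adds 1/(0.5·|P1−P0|) per group.

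For calculation 3:
- A = 1.960·√(0.22 × 0.78 × 4) = 1.624
- B = 0.842·√(0.42 + 0.2408) = 0.684
- C = 0.16² = 0.0256
- N = 2.308²/0.0256 = 208, or 104 per group
- Correction = 1/(0.5 × 0.16) = 12.5, rounded to 13, so 117 per group and 234 in total

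Calculations 1 and 2 give N = 61.3 and 442.1, with corrections of 5.8 and 28.6 per group. These match the printed tables. The planned 240 is 234 rounded up.

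**2. The mean.** Uncorrected, (62 + 442)/2 = 252; corrected, (74 + 500)/2 = 287. So 240 is 12/252 = 4.8% below the first and 47/287 = 16% below the second. Enrolling the mean would not protect the low scenario either: power at 0.04 versus 0.11 is 56% with 252 patients and 62% with 287.

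**3. The rates.** The source rates average (0.217 + 0.04)/2 = 0.1285 and (0.559 + 0.11)/2 = 0.3345, a difference of 0.206. The planning difference is 0.30 − 0.14 = 0.16, which is 0.16/0.206 = 78% of that. The planning pair therefore assumes a smaller contrast than the average TNBC-based one. At the mean rates a total of 130 would suffice uncorrected (150 corrected).

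**4. Power at 120 per group.** Power = Φ{[d − 1.960·√(2P(1−P)/n)] / √[(P1(1−P1) + P0(1−P0))/n]}, where d = |P1−P0|, reduced by 1/n for the corrected version. For 0.14 versus 0.30, uncorrected: (0.16 − 0.1048)/0.0525 = 1.05, and Φ = 0.854.

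| P0 | P1 | Power | Power, corrected |
|---|---|---|---|
| 0.14 | 0.30 (planning pair) | 85% | 81% |
| 0.1285 | 0.3345 (mean source rates) | 97% | 96% |
| 0.04 | 0.11 (calculation 2) | 54% | 44% |
| 0.217 | 0.559 (calculation 1) | >99.9% | >99.9% |

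**5. A receptor-mixed hereditary group.** Assume a share f of carriers has the TNBC rate and the rest have P0; the documents give neither f nor the non-TNBC carrier rate. At f = 0.5, calculation 1 becomes P1 = 0.388 with 83% power (79% corrected), and calculation 2 becomes P1 = 0.075 with 21% (14%). Diluting 0.30 in the same way would give 36% (30%) at f = 0.5. That step is not legitimate, because the third calculation states 0.30 for the hereditary group as a whole and does not attribute it to TNBC.

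**6. Cut-off.** Moving from 5% to 25% lowers the proportion called high; allowing immune cells to qualify raises it. The documents do not say which effect is larger, so no loss of power can be inferred.

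**7. Relative risk.** 0.30/0.14 = 2.143, not 2.114. The printed odds ratio is right: (0.30/0.70)/(0.14/0.86) = 2.633. The relative risk enters no formula.

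**The case for a change.** The best argument for acting is that the section never shows the power of 240 outside its own assumption. Across the plan's literature pairs that power runs from about even odds to near certainty, and the low figure needs no assumption from outside the documents. The proxy argument is also logically sound for calculations 1 and 2, and disclosing a weak proxy does not measure its effect. A short table of power or detectable rates would cost nothing. With 120 per group and the continuity correction, the P1 detectable with 80% power is about 0.30 if P0 is 0.14 and about 0.155 if P0 is 0.04.

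All of that stands as commentary. None of it shows that the plan fails to deliver what it states. Calculations 1 and 2 mark out a range; the size comes from calculation 3, which makes no claim to be a TNBC rate. The low pair is one end of that range and should not be cited without the other. The safeguard against misreading a null result is already in section 13.4, which specifies logistic regression with an odds ratio and 95% confidence interval. That interval will show which effects remain compatible with the data, whatever was assumed at planning.

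**Conclusion.** No change is needed. The arithmetic is right, and 240 patients give 81–85% power at the rates on which the size rests, which meets the stated 80%. That conclusion is conditional on 0.14 versus 0.30, which is a planning judgement made where the section says exact data are lacking. Choosing a pair between two widely separated literature anchors is a fair trade-off: covering the lower anchor would take 442 to 500 patients, and the higher needs only 62 to 74.

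The remaining defects are clerical or explanatory. The sentence about the mean describes 240 poorly, since the means are 252 and 287. The planning pair has no stated derivation. The relative risk is misprinted. Correcting these would leave the sample size, the analysis and the result as they are. A reader of the final report should bear in mind that power was about even, or slightly below, if the true rates are near 0.04 and 0.11.

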## **Study design**

This is a multicentre, non-interventional, prospective study to be carried out in representative oncology departments / institutions in order to determine the association between the presence of germline DNA-repair genes mutations and PD-L1 expression level in tumour and immune cells in breast cancer. No additional procedures besides those already used in the routine clinical practice will be applied to the patients. Treatment assignment will be done according to the current practice.

It is planned to enroll approximately 240 subjects in Russian Federation.

PD-L1 expression in tumor and immune cells in FFPE tumor tissue samples is the primary variable in this study.

Genetic testing of germline mutations in DNA-repair system genes (NGS) in blood samples receiving on Screening/ Baseline Visit and PD-L1 expression testing (IHC) in FFPE tumor tissue samples will be carried out in Republican Clinical Oncological Dispensary, Kazan.

The investigated group will consist of patients with clinical features of hereditary BC and revealed pathogenic germline mutations in DNA-repair genes (TP53 MLH1 MSH2 MSH6 PMS2 EPCAM APC MUTYH CDKN2A CDK4 ATM KIT PDGFRA CDH1 CTNNA1 PRSS1 SPINK1 BRCA1 BRCA2 FANCI FANCL PALB2 RAD51B RAD51C RAD54L RAD51D CHEK1 CHEK2 CDK12 BRIP1 PPP2R2A BARD1 PARP1 STK11 XRCC3). The control group will consist of patients with sporadic BC without mutations in these genes.

The PD-L1 expression level in tumor and immune cells and number of TILs in FFPE tissue samples received prior to start of any antitumor treatment will be estimated in both groups.

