## 1. INTRODUCTION

### 1.1 Background

Breast cancer (BC) occupies the first place among malignancy in females (29.9% of all tumors in female patients in Russian Federation in 2015) [1].

One of the most perspective direction of the oncotherapy is anticancer immunotherapy – employment of inhibitors of immune checkpoints. Immune checkpoints inhibitors (such as anti-PD-1 and anti-PD-L1 antibodies) have shown good clinical efficiency in clinical research to cure such malignant tumor with high mutation load, as melanoma, lung cancer, and others.

One of the hypothesis of such effect states that, usually, more cancer neoantigens are synthetized in the tumors with high mutation load (driven by genome instability), causing severe lymphoid infiltration [2-3]. This situation is balanced by overexpression of such inhibitors of the immune response as PD-1 and PD-L1 [4 - 6].

Breast cancer – is relatively heterogenic tumor, with different genetic, morphological and phenotypic forms.

Despite relatively low expression of PD-L1 in BC in general, there are reasons to believe that genetic instability, driven by mutations in genes involved in DNA repair, can increase the immunogenicity and, thus, the expression of PD-L1 in BC.

To date, it is widely accepted that 5-10% of BC cases are represented by hereditary types, i.e. mediated by germline pathogenic mutations in genes of DNA reparation pathways. Hereditary breast cancer (HBC), as well as ovarian cancer (OC), caused by mutations in genes BRCA1, BRCA2, CHEK2, TP53 и PTEN, and others. Thus, one of the promising directions here is to understand the inter-relation among germline pathogenic mutations associated with HBC, and activity of PD-L1. It would allow to optimize selection of anti-PD-L1 therapy, by forming group of patients (matching criteria of HBC) with high level of PD-L1 expression in cancer cells and tumor-infiltrating lymphocytes.

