## **2. NIS OBJECTIVES**

### **2.1 Primary objective**

To reveal association between the presence of germline DNA-repair genes mutations and PD-L1 expression level in tumour and immune cells in breast cancer (to reveal the difference of PD-L1 high tumor rate between patients with hereditary BC who have clinically significant germline mutations in DNA-repair genes (HR- deficiency) and patients with sporadic BC without such mutations).

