## **4.2 Inclusion criteria**

The subject population must fulfil all of the following criteria:

1. The voluntary obtained informed consent signed by both the subject and the investigator.
2. Females 18 years age or more.
3. Histologically confirmed BC with known hormone receptors and HER2neu receptors status, Grade of tumor, diagnosed before enrolment into the study.
4. Availability of FFPE tissue samples received prior to any type of antitumor treatment start. Tumour tissue samples must be satisfied IHC requirements for PD-L1 testing.
5. Ability of blood samples receiving for NGS germline mutations testing.
6. Completed medical records (stage, receptors status, demographic data)

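### Does section 14 need separate testing numbers for familial and sporadic patients in place of one total near 390 and one 35-40% failure rate?

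*Combined protocol and SAP*

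**What the plan says.** Section 14 sets the target at about 120 mutation carriers and about 120 patients without mutations, and then turns to screening: "We will need to test near 390 patients for enrolling 240 patients (expected screen failure rate 35-40" per cent). It gives one total and one rate, with no split by group. On the source it says "This data are based on the results of own pivotal study", and the single result it takes from that study is the "frequency of clinically significant mutations in genes of DNA-repair system in familial BC 65" per cent.

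Section 13.3 recruits the groups 1:1 from different populations. Cases need clinical features of hereditary disease (listed in Attachment 3) and a pathogenic germline mutation. For controls it says "The control group will be consisting of patients with sporadic BC without germline mutations in DNA-repair genes". The synopsis (Study design) is similar: "The control group will consist of patients with sporadic BC without mutations in these genes". The primary objective in section 2.1 is narrower. Having named carriers of clinically significant mutations, it compares them with "patients with sporadic BC without such mutations".

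No section gives a mutation rate for sporadic disease. The nearest figure is in section 1.1, which says that "5-10% of BC cases are represented by hereditary types, i.e. mediated by germline pathogenic mutations in genes of DNA reparation pathways"; that refers to all breast cancer. Section 4.2 adds an entry condition unrelated to genotype: "Tumour tissue samples must be satisfied IHC requirements for PD-L1 testing". Table 1 places the IHC work one month after the sequencing result.

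**The concern.** The lower end of the 35-40% range is the complement of the 65% yield, so it looks as if a carrier-finding rate from familial patients has been applied to everyone. For cases, a negative test is a screen failure. For controls, a negative test is what qualifies them. A 35% negative rate in familial disease therefore gives no information on how many sporadic patients will fail.

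If the total were misjudged, sites would not know how many patients of each kind to test within the planned year, and observed screening losses could not be compared with an expectation for each group. A serious shortfall in carriers would threaten the 1:1 enrolment and hence the power of the primary comparison. The looser control wording in section 13.3 and the synopsis adds to the doubt. Taken literally, any variant on the 35-gene panel would disqualify a control.

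**Working it through.** **Inputs from section 14:** 240 to enrol, 120 per group; near 390 to test; 35-40% failure; 65% yield in familial disease; P0 = 0.14, P1 = 0.30, two-sided alpha 0.05, power 80%.

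**Assumptions (not in the documents):** control failure of 0-10%, with the 5-10% hereditary share of all breast cancer in section 1.1 as a guide only; a 60% yield as a lower variant, matching the 40% end of the failure range; non-genetic losses of 10-20%.

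**1. The plan's own figures.** Tests = enrolled / (1 - failure rate).
- 240/0.65 = 369.2, so 370; 240/0.60 = 400. The stated 390 lies between them.
- 1 - 240/390 = 38.5%, inside 35-40%.

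The total and the rate agree with each other. The 65% yield alone, applied to all 240, gives 370 and not 390, so it cannot be the whole source of the figure.

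**2. Split by group.**
- Familial: 120/0.65 = 184.6, so 185; at a 60% yield, 120/0.60 = 200.
- Sporadic at 0%, 5% and 10% failure: 120, 127 and 134 (120/0.95 = 126.3; 120/0.90 = 133.3).

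| Yield | Total tests (control failure 0-10%) | Overall failure, 1 - 240/total | Further loss to reach 390, 1 - total/390 |
|---|---|---|---|
| 65% | 305-319 | 21-25% | 22-18% |
| 60% | 320-334 | 25-28% | 18-14% |

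Put another way, 390 - 185 = 205 tests would be left for 120 controls, a failure rate of 1 - 120/205 = 41.5% (36.8% at the 60% yield: 390 - 200 = 190). Genotype alone does not explain that on any figure in the documents.

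**3. Can ordinary losses fill the gap?** Apply an assumed non-genetic loss to both groups at the 65% yield, dividing each group's requirement by (1 - loss):
- 10%: 340-355
- 15%: 360-375
- 20%: 381-398

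The 20% case contains 390. As an example, 120/(0.65 × 0.80) = 231 familial plus 120/0.80 = 150 sporadic gives 381.

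**4. Does anything depend on 390?** The group size comes from the third calculation in section 14: 104 per group uncorrected and 117 with continuity correction (234 in total). A recalculation gives 105 and 117. At 120 per group, the uncorrected z for power is [0.16 × √120 - 1.96 × √(2 × 0.22 × 0.78)] / √(0.30 × 0.70 + 0.14 × 0.86) = (1.753 - 1.148)/0.575 = 1.05, or about 85% power. The testing total does not enter. The logistic regression in section 13.4 does not use it either, and no rule in the protocol acts on a screen-failure rate.

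**The case for a change.** The strongest case for a change is that the section offers one number as evidence and that number concerns one group. Cases and controls come from different populations at two centres in about a year, and two or three sentences would give sites a target for each. The observation stands: the derivation is not shown, and the non-genetic allowance is neither stated nor sourced.

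A second argument is stronger. Section 4.2 does not require familial features. If unselected patients were tested, a 5-10% yield would mean 120/0.10 = 1,200 to 120/0.05 = 2,400 tests for 120 carriers, and 390 would fall far short. However, section 13.3 defines cases by hereditary features, Attachment 3 lists those features, section 3.1 has family history taken at the visit, and section 14 itself reasons from familial disease. A site following the protocol would sort candidates before testing.

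Third, the number of familial patients tested is the denominator for the secondary objective on mutation frequency. That is true, but the plan sets no precision target. At 185 tested and 65%, the 95% half-width is 1.96 × √(0.65 × 0.35/185) = 6.9 percentage points; at 231 tested it is 6.2. The actual denominator will be known, and section 13.2 already plans to describe history for everyone screened.

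On the control wording, section 13.3 sets controls directly against carriers of pathogenic mutations, and the primary objective makes the contrast explicit. An analyst would read all three places as meaning clinically significant mutations. This is loose drafting and does not create a second definition.

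**Conclusion.** No change follows. Section 14 leaves out a split by group and an explicit allowance for other losses, but its figures agree with each other and 390 is within reach of plausible assumptions. The unexplained part is about 14-22% of the tests, at a yield of 60-65% and an assumed control failure of 0-10%. Tissue unsuitable for IHC and the other criteria in sections 4.2 and 4.3 could account for it, and the sponsor's own study, which is not shown, may hold the data.

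It would be wrong to call 390 a clear overestimate, since an assumed 20% non-genetic loss takes the requirement to 381-398. It would be equally wrong to call it a shortfall, provided candidates are sorted by familial features before testing. The figure is an approximate logistic estimate. Enrolment is defined by about 120 per group, and the power and the primary analysis are the same whether 320 or 400 patients are tested to get there. Writing out the derivation would be tidier but would alter no result or conclusion.
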